- 3) Replacement of the primary imputation approach by the realistic approach (LTFU have the same rate of relapse as completers: $P_S = 1 P_R$).
- 4) Replacement of the mITT by the per-protocol set of patients.
- 5) Replacement of the mITT by the set of completers. This analysis avoids any imputation but is based on a subset of patients. The result should be close to the third sensitivity analysis if there are not many patients with unconfirmed status.

Justification of the non-inferiority margin

The non-inferiority margin of 7% has been defined after consultation with experts. It is justified by the following advantages of the tested combination arm over the reference arm: replacing SSG with oral MF will improve treatment safety by removing the toxic antimonial component of the current SSG-PM treatment; it will be a more patient-friendly treatment by replacing one of the two daily injections with an oral administration; and hospitalization time will be reduced by at least 3 days. Finally, the new combination will ensure suitability in remote areas where VL occurs.

Shift from non-inferiority to superiority

If the tested combination is significantly non-inferior to the reference arm, the test of superiority will be performed (Likelihood ratio test) without adjustment of type error.

Confidential Page 57 of 68

The result of this test as well as the 95% confidence interval of the excess success rate will be used to assess the benefit risk of the tested combination with regards to the reference arm but not to claim the superiority. The analysis will be the same as the primary analysis after replacing the non-inferiority test by the superiority.

Interim analysis

No interim analysis (IA) will be performed in this trial.

10.7. Safety Analysis

All patients enrolled and who received at least one dose of study medication (mITT set of patients) will be included in the safety analysis (treatment-emergent AEs). The incidence rate of the most pertinent and frequent ADR (> 5%) of each treatment group will be compared and tested. No adjustment for multiplicity will be performed. These results will be used for assessing the benefit risk ratio.

The proportion of patients with SAE and/or AEs leading to treatment discontinuation will be described per System Organ Class (using preferred terms defined by MedDRA), and summarised according to relationship to treatment and severity (CTCAE, version 4.03). In addition, a narrative for each of the SAE and AE leading to treatment discontinuation will be developed describing all aspects of the medical event.

The proportion of patients presenting at least one treatment emergent AE (TEAE) will be presented. All TEAEs will be described per study arm using the same classification as presented above. AEs will be tabulated by severity (CTCAE V4.03), and causality.

Abnormalities of laboratory/procedures results will be tabulated with respect to clinical significance. In addition, shift tables and graphs will be generated to describe the laboratory parameter values over time, per treatment arm.

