Pregnancy test ²	Χ					X	X	Х
Spleen/bone marrow/lymph node aspiration, parasitology assessment (microscopy)	X					Х	X ⁵	X ⁵
Hematology (hemoglobin, WBC with differential, platelets)	X		х	Х	Х	Х	X	Х
Biochemistry analysis (AST/ALT, bilirubin, creatinine)	Х		Х	Х	Х	Х		
Biochemistry analysis (Albumin)	X					Х		Х
ECG ³	Х			Х	Х	Х		
Assessment for PKDL	Х					X	X	Х
Blood sample for miltefosine PK ⁴					X	X	X	
Tissue (bone marrow/spleen/lymph node) and blood sample for PD (qPCR)	Х					х	X ⁵	X ⁵
Treatment arm 1		PM QD/MI	= allometric					
Treatment arm 2 – Discontinued						for 28 days		
Treatment arm 3			SSG/PM Q					
Safety assessment	SAEs/non- serious study related AEs		S F	AEs and AE	s monitorin	g during the stu	ıdy	

Confidential Page 29 of 68

- ¹HIV test at D210 will be done only for patients in Gondar and Abdurafi.
- ²Only for woman of child-bearing potential.
- ³ ECG will be performed at baseline and at D14 in all arms, and in addition at D7 and D28 in the reference arm SSG/PM.
- ⁴MF PK assessments at D14 will apply to all patients enrolled in arm 1, while D28 and D56 samples will apply to all patients enrolled in arm 1 and 2. MF PK sample will be collected prior to the morning dose at D14 and D28 (arm 2). D28 (arm 1) and D56 samples will be collected in the morning.
- ⁵ Parasitology and collection of tissue and blood samples for qPCR will be done during the follow-up period after D28 (at D56 and D210) only if clinically indicated (i.e. anytime if suspect of relapse, with reappearance of symptoms and signs of VL).

Total volume of blood to be collected for patient not included in the intensive PK/PD cohort:

Assumptions: Ht= 1mL EDTA, BQ= 2mL dried tube, MF PK= 2mL EDTA, PD= 1mL EDTA. Volume of blood to be collected will be minimized as much as possible, according to the volume of tubes available in the market. The maximum volume to be collected at each study visit will be 6mL.

General note: PK and PD assessments in this schedule of events do not apply to patients included in the intensive cohort (see section 5.1 Schedule of PK/PD events – Intensive cohort).

Confidential Page 30 of 68

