8.5. Assessment of Safety

Safety of the different treatment regimens will be assessed through routine monitoring of adverse events. At each study visit, the patients will be enquired about current adverse events or any events observed during the period previous to the visit. In addition, evaluation of hematology and blood chemistry parameters, regular measurement of vital signs and physical examinations will be made at scheduled follow-up visit.

Audiometric test will be performed at baseline and on days 14, 28 and 210 for all patients.

ECG will be performed at baseline and on day 14 in all arms, and in addition on days

Confidential Page 45 of 68

7 and 28 in the reference arm SSG/PM. SOPs will be developed to guide investigators on audiometry and ECG assessments.

Urine pregnancy tests will be performed in woman of child-bearing potential at baseline to exclude any pregnancy, and on D28, D56 and D210 visits to monitor eventual unexpected pregnancy.

HIV test will be repeated at the D210 visit only for patients in Gondar and Abdurafi sites, due to high prevalence of HIV/VL co-infected patients (15%) in this specific population.

The frequency and severity of AEs will be described, as well as frequency of SAEs or AEs that lead to treatment discontinuation. See section 8.6 for AE definition and reporting.

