8.6. Adverse event definitions and reporting

8.6.1. Adverse Event definition

Any untoward medical occurrence in a clinical trial subject administered a medicinal product and which does not necessarily have a causal relationship with this treatment.

It can therefore be any unfavourable and unintended sign (e.g. an abnormal laboratory finding), symptom, or disease temporally associated with the use of a medicinal product, whether or not considered related to the medicinal product.

Definition of an AE includes worsening (in severity and frequency) of pre-existing conditions ("Medical history") before first Investigational Medicinal Product (IMP) administration and abnormalities of procedures (i.e. ECG, X-ray...) or laboratory results which are assessed as "clinically significant" (see details in section 8.6.2).

What is not an AE?

Confidential Page 46 of 68

- Medical conditions present at the initial study visit that do not worsen in severity or frequency during the study are NOT considered as AE.
- Symptoms, exacerbation or worsening of the studied disease will NOT to be considered as AE nor captured on the AE page of the CRF if consistent with the anticipated natural progression of the disease (overall and for this given subject).
- Lack of efficacy of the IMP is NOT considered as AE.

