8.6.7. Adverse Event reporting requirements

Confidential Page 49 of 68

Information on adverse events must be evaluated by a physician. Each adverse event is to be classified by the investigator as serious or non-serious. This classification will determine the reporting procedure for the event to DNDi and Health Authorities/Ethics Committees (as per local regulatory requirements).

All serious adverse events (SAE) are to be reported immediately (within 24 hours of awareness of SAE by the investigator) to DNDi ([contact]), using the SAE report form. This includes a description of the event, onset date and seriousness criteria, duration, severity, relationship to study drugs, outcome, measures taken and all other relevant clinical and laboratory data. The initial report is to be followed by submission of additional information (follow-up SAE form) as it becomes available. Any follow-up reports should be submitted as soon as possible, and if possible within 5 working days.

In addition to immediately reporting SAEs to DNDi, Investigators are responsible for reporting SAEs occurring at their site to the Ethics Committee (IEC), and any periodic safety reporting if applicable, in compliance with the local regulatory requirements.

Serious adverse events should also be reported on the clinical trial adverse event case report form (CRF). It should be noted that the form for reporting of SAE (SAE form) is not the same as the adverse event section of the CRF. Where the same data are collected, the two forms must be completed in a consistent manner, and the same medical terminology should be used.

Non-serious adverse events are to be reported on the CRF, including description of the event, onset date, duration, severity, seriousness, relationship to all study drugs, actions taken and outcome. In the CRF, a given adverse event will be recorded only one time per patient, and the severity recorded will be the maximum level reached. If several distinct episodes of the same condition occur, their number will be recorded in the CRF.

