8.6.9. Adverse Event causality assessment

For both serious and non-serious adverse events, the investigator is required to assess if there is a causal relationship between the adverse event and all the study drugs, i.e. to determine whether **there is at least a reasonable possibility** that one of both study drugs caused or contributed to the adverse event. This means that there are facts and arguments to suggest a causal relationship.

To help investigators with the decision binary tree in the evaluation of causality, the CIOMS VI group recommends that investigators be asked to consider the following before reaching a decision:

- Medical history
- Lack of efficacy/worsening of existing condition
- Study medications
- Other medications (concomitant or previous)
- Withdrawal of study medication, especially following trial discontinuation / end of study medication
- Erroneous treatment with study medication (or concomitant)
- Protocol related procedure

Using this information the investigator will classify each adverse event as:

Not related: There is no reasonable possibility of causal relationship

between an AE and study drug

Related: There is at least a reasonable possibility of a causal relationship

between an AE and a study drug. This means that there are facts

(evidence) or arguments to suggest a causal relationship.

The decision to suspend, and resume treatment or to permanently interrupt treatment due to an adverse event will be left to the clinician in charge.

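### Section 10.7 would compare an ECG-detected ADR over three scheduled post-baseline ECGs in arm 3 and one in arm 1, which overstates the difference by a modest, unknown amount; a low-priority D14 estimate would show it

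*Combined protocol and SAP*

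**What the plan says.** The ECG schedule is in section 5 (Schedule of events, footnote 3): "ECG will be performed at baseline and at D14 in all arms, and in addition at D7 and D28 in the reference arm SSG/PM". Section 8.5 repeats it: "ECG will be performed at baseline and on day 14 in all arms, and in addition on days", with the sentence running on to days 7 and 28 for the reference arm. The two places agree.

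An ECG finding becomes an adverse event if it is assessed as clinically significant: section 8.6.1 includes "abnormalities of procedures (i.e. ECG, X-ray" and the like in the definition. It counts as related when "There is at least a reasonable possibility of a causal relationship" (section 8.6.9), as judged by an investigator who knows the treatment (section 7.6).

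Section 10.7 then plans the between-arm test: "The incidence rate of the most pertinent and frequent ADR (> 5%) of each treatment group will be compared and tested". There is no adjustment for multiplicity. On use, it says: "These results will be used for assessing the benefit risk ratio". Procedure abnormalities are to be tabulated by clinical significance, with no visit mentioned. Displays over time are specified for laboratory values: "shift tables and graphs will be generated to describe the laboratory parameter values over time".

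**The concern.** A patient in arm 3 has three scheduled chances to show an ECG abnormality after baseline, and a patient in arm 1 has one. Incidence counted over all visits rises with the number of looks, so part of any arm 3 excess in an ECG-detected ADR would come from the schedule. The extra looks can only add arm 3 findings, so the error favours MF/PM.

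The domain matters, because the protocol summary names cardiotoxicity as an SSG toxicity and section 10.7 feeds the comparison into benefit-risk. Section 10.7 does not ask for the one comparison made on equal terms, D14 against baseline in both arms.

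The issue is confined to findings from scheduled ECGs. Audiometry, haematology and biochemistry fall on the same days in all arms (sections 5, 8.5 and 8.5.1), and events that present with symptoms do not depend on the ECG calendar.

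**Working it through.** The plan gives no figure for this comparison, so there is none to reproduce.

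**Inputs from the documents.** Scheduled post-baseline ECGs: 3 in arm 3 and 1 in arm 1 (sections 5 and 8.5). Patients per compared arm: 170 (section 10.1). Listing threshold: above 5%, i.e. at least 9 of 170 (9/170 = 5.3%; 8/170 = 4.7%).

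**Assumptions (not in the documents).** A probability q that one ECG shows a recordable related finding, the same on each ECG day within an arm: q1 in arm 1, q3 in arm 3. Within-patient correlation ρ of 0, 0.3, 0.5 or 0.7 (beta-binomial), where a higher ρ means findings persist. Pooled two-sided 5% z test, run only if either arm exceeds 5%.

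**Chance of at least one finding.**

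- Two ECGs: P2(q) = 1 − (1−q)[1−q(1−ρ)]
- Three ECGs: P3(q) = 1 − (1−q)[1−q(1−ρ)][1−q(1−ρ)/(1+ρ)]

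**Step 1: overstatement.** The planned difference is P3(q3) − q1. With three ECGs in both arms it would be P3(q3) − P3(q1). The overstatement is therefore P3(q1) − q1, whatever the arm 3 rate.

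Example with q1 = 2%, ρ = 0.3: P3 = 1 − 0.98 × 0.986 × 0.98923 = 4.41%, so the overstatement is 2.41 points.

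D28 falls after treatment in both arms: 28 − 14 = 14 days after the end in arm 1 and 28 − 17 = 11 days in arm 3. If D28 adds no related findings, the overstatement is P2(q1) − q1 = q1(1−q1)(1−ρ). In the same example this is 0.02 × 0.98 × 0.7 = 1.37 points.

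Overstatement in percentage points, ρ = 0 / 0.3 / 0.5 / 0.7:

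| q1 per ECG | D28 counts fully | D28 adds nothing |
|---|---|---|
| 0.5% | 0.99 / 0.62 / 0.41 / 0.24 | 0.50 / 0.35 / 0.25 / 0.15 |
| 2% | 3.88 / 2.41 / 1.63 / 0.93 | 1.96 / 1.37 / 0.98 / 0.59 |

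At 0.5% the largest value is 0.0099 × 170 = 1.7 patients. If findings persist fully (ρ = 1) it is zero.

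**Step 2: a true SSG excess (0.5% vs 3% per ECG).** Exact enumeration of two binomials of 170 gives this chance of a significant result:

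| Schedule | ρ = 0 / 0.3 / 0.5 / 0.7 |
|---|---|
| As planned (3 vs 1 ECGs) | 96 / 78 / 56 / 32% |
| Three ECGs in both arms | 89 / 72 / 53 / 31% |

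The unequal schedule adds 1 to 7 percentage points to the detection of a real effect.

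**Step 3: false significance when both arms have the same rate.**

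| q per ECG, both arms | D28 counts fully | D28 adds nothing |
|---|---|---|
| 0.5% | at most 0.1% | 0.0% |
| 1% | 5.7 / 1.2 / 0.3 / 0.1% | 0.6 / 0.2 / 0.1 / 0.0% |
| 2% | 42.6 / 17.9 / 8.2 / 3.0% | 11.8 / 5.9 / 3.3 / 1.7% |
| 3% | 62.5 / 33.1 / 18.4 / 8.6% | 24.3 / 14.4 / 9.2 / 5.4% |

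**Step 4: can D14 alone replace the planned test?** No. At 0.5% vs 3%, a D14-only test detects the excess in 42% of trials, or 7% if the 5% threshold also applies. The 95% CI half-width would be about 1.96 × √(0.005×0.995/170 + 0.03×0.97/170) = 2.8 points around a true difference of 2.5.

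**The case against.** The strongest reply is that the large error rates in step 3 need three things at once: equal ECG risk in both arms, at least about 2% per ECG, and transient findings (the highest figures also need a D28 ECG that carries full risk). The documents point the other way. They name cardiotoxicity for SSG, list no cardiac effect among the main effects of MF or PM (section 1), and exclude patients with a clinically significant abnormal ECG at entry (section 4.2). If tests are run by preferred term, each term must exceed 5% alone. This stands, and it limits the point to a modest overstatement of size. The D28 part is less certain for MF: section 1 gives a 7-day half-life, so D28 in arm 1 is only two half-lives after the last dose.

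A second reply is that the data to separate the visits are collected. Section 8.6.7 records onset date and duration for each event, and section 10.7 does not rule out tabulating ECG by visit. Section 10.2 also refers to a statistical analysis plan whose text was not available for this review, so a D14 comparison there cannot be excluded. This also stands: the gap is in what section 10.7 specifies and not in what could be produced.

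A reader might infer that the schedule puts the non-inferiority conclusion or the 7% margin in doubt, since better safety is part of the margin's justification in section 10.6. The documents do not support that. The margin was fixed in advance on the removal of the antimonial, and no ECG result enters it or the primary analysis.

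**Conclusion.** The point holds as a conditional, low-priority one. If an ECG-detected ADR exceeds 5% and is tested, section 10.7 would overstate the arm 3 minus arm 1 difference. The assumed rates put this at about 0.2 to 1.0 points at 0.5% per ECG in arm 1 and 0.9 to 3.9 points at 2%, or 0.15 to 0.5 and 0.6 to 2.0 points if D28 adds no related findings. These figures rest on assumed rates, correlation and a constant risk per ECG; the documents fix only the count of ECGs and the number of patients.

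It would go too far to say that the plan is likely to produce a spurious cardiac safety advantage for MF/PM. That requires similar rates of about 2 to 3% or more per ECG in both arms with transient findings, and nothing in the documents makes this likely. Where SSG truly carries more ECG toxicity, the planned test reaches nearly the same conclusion as it would with equal schedules.

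**What to change.** Leave the ECG schedule and the planned all-ECG test as they are. Add to section 10.7, unless the separate analysis plan already covers it:

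> For any ECG-detected ADR compared between arms 1 and 3, ECG findings are also tabulated by visit (D7, D14, D28), and the difference with 95% CI is reported for the common schedule (D14 against baseline). A patient counts if the D14 ECG shows a new or worsened, clinically significant, related finding, whatever its onset date. Patients with no D14 ECG are listed. The benefit-risk text states how much of any excess comes from the arm 3-only ECGs.

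The onset-date clause is needed because "a given adverse event will be recorded only one time per patient" (section 8.6.7): an arm 3 finding first seen on D7 and still present on D14 would otherwise drop out of the D14 count. The common-schedule estimate is descriptive, with no added significance test.

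The cost is a few sentences and one table. The downside is that the D14 estimate is imprecise and sets the end of treatment in arm 1 against day 14 of 17 in arm 3. It belongs beside the all-ECG comparison and should not replace it.

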2.2.2. Secondary Endpoint(s)

Safety:

Frequency of SAEs and AEs requiring treatment discontinuation.

Frequency and severity of adverse events from the start of treatment through the last visit, at D210.

Efficacy:

Initial cure - cure at the end of treatment (Day 28), defined as recovery of clinical signs and symptoms; absence of parasites (microscopy) and no rescue treatment administered up to and including Day 28.

Probable cure - absence of clinical signs and symptoms of VL at D56 and no prior requirement for rescue treatment.

Pharmacokinetics:

Total and partial blood plasma exposure to PM and MF (bioanalysis performed by a validated LC-MS/MS assay), defined as the area under the concentration-time curve, for MF, during treatment and until the last point of follow-up, and for PM based on full curves both on the first day of treatment (day 1) and the last day of treatment (day 14).

Pharmacodynamics:

Blood parasite clearance over time (qualitative and quantitative), as measured by qPCR from blood samples, from baseline until day 210, and at any suspicion of relapse during the trial.

Tissue parasite loads, as semi-quantified by microscopy and qPCR from tissue samples collected at baseline, at the end of treatment (D28) and at any suspicion of relapse during the trial.

 Compliance to MF treatment in an outpatient setting will be described through patients' hospital records history, drug accountability and PK measurements.

3. Study design and study design rationale

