7.6. Blinding and procedures for unblinding

This is an un-blinded open label study.

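### The only safety comparison that is tested between arms rests on ADRs, an undefined term that most naturally means events judged related by an unblinded investigator, while the safety endpoints count events regardless of cause

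*Combined protocol and SAP*

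**What the plan says.** **The test.** Section 10.7 states: "The incidence rate of the most pertinent and frequent ADR (> 5%) of each treatment group will be compared and tested". It continues "No adjustment for multiplicity will be performed" and "These results will be used for assessing the benefit risk ratio". No significance level or test statistic is given for this comparison.

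**The rest of 10.7 is descriptive.** For all-cause events the plan says "The proportion of patients presenting at least one treatment emergent AE (TEAE) will be presented" and "All TEAEs will be described per study arm using the same classification as presented above". SAEs and AEs leading to discontinuation are described by System Organ Class with narratives. AEs are tabulated by severity and causality. Laboratory results get tables of clinical significance, shift tables and graphs.

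**The endpoints.** Section 2.2.2 lists two safety endpoints: the frequency of SAEs and of AEs requiring treatment discontinuation, and "Frequency and severity of adverse events from the start of treatment through the last visit, at D210". Neither is limited to related events.

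**Who decides relatedness.** Under 8.6.9 the investigator classifies each event as related or not related. The threshold is "Related: There is at least a reasonable possibility of a causal relationship". Section 7.6 states "This is an un-blinded open label study". The protocol describes no blinded or independent causality review.

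**The term.** ADR does not appear in the abbreviation list, which has only AR for adverse reaction, and it is not defined elsewhere in the document.

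**The concern.** The quantity tested is not the quantity declared as the endpoint. Between the two lies a yes/no judgement made by someone who knows the arm.

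That judgement is open to expectation here. The protocol presents SSG as the toxic component (sections 1 and 10.6) and miltefosine as well tolerated (section 1). Section 8.6.2 itself gives anaemia early in treatment as a finding that may reflect the disease. The same event can reasonably be put down to drug or to disease, and the choice may differ by arm.

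At stake is the safety half of the benefit-risk statement. Better safety is one of the advantages listed in 10.6 to support the 7% margin, and section 1 says the data will go to ministries of health and regulators. A tested difference that attribution alone can produce, or remove, is a weak basis for that statement. The primary efficacy result is not affected.

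**Working it through.** The plan gives no expected rate, power or significance level for the safety test, so there is no figure to reproduce. The check has two parts.

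**1. Tested quantity against endpoint**

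| Item | Causality condition | Between-arm test stated |
|---|---|---|
| Frequent ADRs, >5% (10.7) | Related only, on the natural reading | Yes |
| All TEAEs (10.7; endpoint in 2.2.2) | None | No |
| SAEs and AEs leading to discontinuation (10.7; endpoint in 2.2.2) | None | No |

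The data for the untested rows are collected: 8.6.6 requires AEs in the reporting period to be reported whether or not they are thought to be related.

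**2. What attribution alone can do to the test**

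Inputs:
- n = 170 per arm (10.1).
- Test: pooled two-proportion z test, two-sided 5%. Assumed, as 10.7 states none.
- True incidence π of one event term, equal in arms 1 and 3. Assumed 20% or 30%.
- Share of events called related, a1 in arm 1 and a3 in arm 3. Assumed.

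Formulas: the ADR rates are p1 = π × a1 and p3 = π × a3. The test is z = (x3/n − x1/n) / √(2p̄(1 − p̄)/n), where x1 and x3 are the numbers of patients with the ADR and p̄ is their pooled proportion. The chance of significance is the sum of Bin(x1; n, p1) × Bin(x3; n, p3) over all pairs with |z| > 1.96.

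| Shares called related, arm 1 vs arm 3 | ADR rates at π = 20% | Significant | ADR rates at π = 30% | Significant |
|---|---|---|---|---|
| 50% vs 50% | 10% vs 10% | 5% | 15% vs 15% | 5% |
| 50% vs 60% | 10% vs 12% | 9% | 15% vs 18% | 12% |
| 50% vs 70% | 10% vs 14% | 21% | 15% vs 21% | 30% |
| 50% vs 80% | 10% vs 16% | 38% | 15% vs 24% | 56% |

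Hand check of 10% vs 16% by the normal approximation:
- Pooled rate 0.13, null standard error √(2 × 0.13 × 0.87 / 170) = 0.0365.
- Standard error under the alternative √((0.10 × 0.90 + 0.16 × 0.84) / 170) = 0.0363.
- (0.06 − 1.96 × 0.0365) / 0.0363 = −0.32, which gives about 38%, in line with the exact sum.

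**Direction.** Exchanging the shares (80% in arm 1, 50% in arm 3) gives the same probabilities with the sign reversed.

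**Hiding a difference.** If true incidence were 20% in arm 1 and 30% in arm 3, with 75% and 50% called related, the ADR rates would be 0.20 × 0.75 = 0.15 and 0.30 × 0.50 = 0.15. A real difference would vanish from the tested comparison.

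**With all-causality TEAEs.** Equal true incidence returns about 5% per term whatever the attribution, provided events are recorded equally in both arms.

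**The case against.** **The term may be loose wording.** The ADR sentence directly follows a mention of treatment-emergent AEs, so the sponsor may have meant AEs. Section 10.2 also refers to a statistical analysis plan that could define the term and is not part of the document reviewed. This stands as a reason to ask for a definition. But 10.7 uses ADR alongside AE and TEAE as if they differed, and 8.6.9 is the only causality rule given.

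**The endpoint is already analysed on an all-cause basis.** The endpoints are frequencies, 8.5 says AE frequency and severity will be described, and 10.7 does this per arm and tabulates by causality. A careful reader could notice an attribution gap. This lessens the problem. It does not change which comparison is tested and sent to benefit-risk.

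**The proposed change does not remove all open-label bias.** This stands. Section 8.6.1 keeps disease worsening that fits natural progression out of the AE record. Section 8.6.2 lets laboratory findings linked to expected VL symptoms go unreported unless they meet its clinical-significance criteria. So part of the disease-or-drug judgement is made before an event becomes a TEAE. Ascertainment also differs by arm: ECGs at D7 and D28 are done only in arm 3 (section 5 and 8.5), and 30 minutes of observation with recording of vomiting is specified for miltefosine doses (7.2.1).

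**A reader might infer that the test is biased against SSG.** The documents do not support that. The protocol's view of SSG makes this direction plausible, but vomiting is a listed main side effect of miltefosine and could readily be called related in arm 1. Both arms also contain paromomycin.

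**A reader might also infer that the non-inferiority margin depends on this test.** It does not. The 7% margin is fixed in advance and also rests on fewer injections, shorter hospitalisation and suitability for remote areas. Under 10.6 the benefit-risk assessment also uses the superiority test result and the 95% confidence interval for the efficacy difference.

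**Conclusion.** The point holds in a limited form. The one tested safety comparison most naturally depends on unblinded causality judgements, does not match the safety endpoints in 2.2.2, and feeds the benefit-risk assessment. Attribution could create or hide a difference in either direction.

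The size in this trial is unknown. At 170 per arm and a true incidence of 20% in both arms, the chance of a significant result per tested term runs from about 9% (50% vs 60% called related) to 38% (50% vs 80%), against a nominal 5%. The lower figure is only modestly above nominal. These values rest on assumed incidence, attribution shares and test level, and on reading ADR as an AE judged related. If the sponsor meant all AEs, the defect reduces to an undefined or wrong term in 10.7, which still needs correcting.

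**What to change.** In section 10.7:

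1. Define ADR, by reference to the related category in 8.6.9 if that is what is meant.
2. Make the arm 1 vs arm 3 comparison the incidence of TEAEs regardless of causality, by preferred term under the same >5% rule. Add SAEs and AEs leading to discontinuation, so that both endpoints in 2.2.2 are covered. Report differences with 95% confidence intervals.
3. Keep the ADR comparison as supportive.
4. Base the benefit-risk statement mainly on the all-causality results.
5. State, when interpreting them, that open-label recording (8.6.1 and 8.6.2) and arm-specific ascertainment (the arm 3 ECGs, and vomiting observation after miltefosine doses) remain.

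The cost is analysis-plan wording and some extra tables from data already collected. There is a small downside: more unadjusted comparisons, and some dilution by unrelated illness up to D210.
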